3.4 Secondary Endpoints

1. Clinical recovery and resolution of COVID-19 symptoms

1a. Sustained recovery and resolution rates of common COVID-19 symptoms:

(i.e., stuffy or runny nose, sore throat, cough, low energy or tiredness, muscle or body ache, headache, chills or shivering, feeling hot or feverish, nausea, vomiting, diarrhea, shortness of breath with exertion; impairment in sense of smell or taste)

Proportion of subjects in treatment group versus placebo group, respectively, who per symptom questionnaire on days 4, 7, 10, 14, 21, 28, 42, 60 post randomization have achieved for two consecutive days:

- o scores not higher than 0 for all symptoms
- o scores not higher than 1 for all symptoms
- o scores not higher than 0 for all symptoms other than impairment of taste or smell
- o scores not higher than 1 for all symptoms other than impairment of taste or smell
- *1b. Sustained improvement of global impression rates:* Proportion of subjects in treatment group versus placebo group, respectively, who per symptom questionnaire on days 4, 7, 10, 14, 21, 28, 42, 60 post randomization have answered for two consecutive days
 - "Yes" to "In the past 24 hours, have you returned to your usual health (before your COVID-19 illness)?"
 - "Yes" to "In the past 24 hours, have you returned to your usual activities (before your COVID-19 illness)?"
 - o "None" to "In the past 24 hours, what was the severity of your overall COVID-19 related symptoms at their worst?"
 - o "Mild" to "In the past 24 hours, what was the severity of your overall COVID-19 related symptoms at their worst?"
- 1c. Time to sustained recovery, resolution or improvement: comparison in treatment group versus placebo group, respectively of the number of days from randomization to the first day of achieving each item in 1a and 1b above.

2. Physical functions and parameters relevant to COVID-19

- **2a. Parameter rates:** Proportion of subjects in treatment group versus placebo group, respectively, who on days 4, 7, 10, 14, 21, 28, 42, 60 post randomization per thermometer or pulse oximeter reading experienced:
 - fever at any point between enrollment and day 2 post randomization and who were afebrile <38C
 - o oxygenation of SpO2>=96% or >93% in room air when resting
- 2b. Time to and length of parameters: comparison in treatment group versus placebo group, respectively of the number of days

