5.2 Study Assessments

Table 1: Schedule of Events: **1** = In-Person; **2** = Telephone; **3** = Subject Self-Tracking

Time Point (Days)	Screen / enroll	D19	D4	D7	D10	D14	D21	D28	D42	D60	ET ¹⁰
STUDY TEAM											
Inclusion / Exclusion	İ										
Consent	İ							\			
Screening Tests ^{1, 12}	İ					1					
Demographics	İ										
CXR or CT ¹³	İ										
Physical Exam	İ			İ		1	Ť	Ţ			ţ
Vitals ²	İ			İ		İ	İ	İ			İ
EKG	İ			İ		İ	İ	İ			İ
CoV-2 N/P ³	İ					İ		Ť			Ť
Standard labs ^{4, 12}	İ			İ		Ì		Ť			Ť
Blood draws ^{5, 12}	İ			İ		1	Ť	Ť			İ
Immunology tests ^{6, 12}	İ			İ		Ì	Ť	Ť			Ť
CoV-2 blood ^{7, 12}								Ť			Ť
AE assessment	İ	2	2	İ	2	Ţ	İ	Ī	2	~	Ĭ
Symptoms assessment	İ	2	2	İ	2	Ţ	İ	İ	2	~	İ
WHO 9-Point Scale ⁸	İ	2	2	İ	2	Ţ	İ	İ	2	2	İ

SUBJECTS (as recorded in study diary)						
IP/placebo intake	Three times per day through day 28 or ET					
Temperature ¹¹	Daily via thermometer through day 28 or ET; subject will report via telephone to					
	study team at Day 42 & 60					
SpO2 resting ¹¹	Daily via pulse oximeter through day 28 or ET; subject will report via telephone to					
	study team at Day 42 & 60					
Symptom tracking	legistrian One time per day through day 28 or ET; subject will report via telephone to study					
	team at Day 42 & 60					

¹Screening tests: HIV, Hepatitis B, Hepatitis C, and pregnancy (serum pregnancy test for women of child-bearing potential per MedStar definition at enrollment and at day 14).

²Vital signs: oral temperature, heart rate, systolic blood pressure.

³Quantitative nasopharyngeal SARS-CoV-2 RNA testing (RT-PCR): nasopharyngeal or throat swabs will be used; any FDA-approved or commercial testing method will be acceptable. A home health agency may be used to confirm COVID-19 by RT-PCR in the subjects' home in the event their initial testing did not include PCR, to ensure expeditious resulting and appropriate inclusion into the trial. If home health is used to collect the PCR test or there is a delay in PCR resulting at initial screening, the subject will return to either MedStar Washington Hospital Center or MedStar Franklin Square for completion of the screening/enrollment visit in 1 to 3 days, once positive PCR is confirmed, to complete all study procedures including randomization and medication dosing under observation. ⁴Standard labs: serum chemistry, coagulation tests and hematology. Pregnancy tests for women of childbearing potential at screening, day 14 and end of treatment.

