5.3 Selection Criteria

Inclusion Criteria:

- Subject (or legally authorized representative) provides written informed consent prior to the initiation of any study procedures.
- Subject understands and agrees to comply with planned study procedures, including using the diary.
- Subject agrees to the collection of nasopharyngeal swabs and venous blood per protocol.
- Subject is male or non-pregnant female adult ≥18 years of age at time of consent.
 - Women with a history of menstruation must agree to use two methods of contraception, at least one of which is highly effective, for the duration of the study as well as to undergo additional pregnancy testing during the study.
- Subject has a laboratory confirmed SARS-CoV-2 infection as determined by RT-PCR assay prior to enrollment.
- Subject has evidence of either mild or moderate COVID-19 illness of less than 7 days from first onset, with minimal baseline symptom severity based on patient-reported FDA scoring system defined as follows:
 - Subject presents with at least two common symptoms of COVID-19 from the following list: stuffy or runny nose, sore throat, cough, low energy or tiredness, muscle or body ache,

⁶Immunology tests: COVID-19 relevant immunology labs (see Appendix 12.1 for complete list). See footnote to Appendix 12.1 as certain labs will be sent to and resulted from outside lab facilities.

⁷Quantitative blood SARS-CoV-2 antibody testing: Blood samples will be used; any FDA-approved or commercial testing method will be acceptable.

⁸WHO 9-point scale: see description of secondary end points for details.

headache, chills or shivering, feeling hot or feverish, nausea, vomiting, diarrhea, shortness of breath with exertion (without supplemental oxygen requirement) with a score of 2 or higher; impairment in sense of smell or taste with a score of 1 or higher **OR**

- Subject presents with any (i.e., at least one) symptom of COVID-19 as defined above AND clinical evidence of moderate COVID-19 as defined by FDA guidance for industry (such as respiratory rate >20 breaths per minute, heart rate >90 beats per minute, with oxygen saturation >93% on room air at sea level).
- Subject presents with high-risk for COVID-19-related inflammation determined by at least one comorbidity, including obesity, diabetes, hypertension, stable heart disease, respiratory disease, and / or non-severe fatty liver disease.

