8.2 Analysis Methods

General Methods

FDA Data Standard Guidelines will be followed. Continuous variables will be summarized using the number of observations, number of observations above the limit of quantification (if applicable), mean, standard deviation (SD) median, and range. Categorical variables will be summarized using frequency counts and percentages. Comparison of belnacasan (VX-765/RVT-201/MSR-001) and placebo groups will utilize Poisson regression for counts, Cox proportional hazards regression for time-to-event data and mixed effects models for continuous and categorical data obtained over study days.

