8.5 Treatment Effect Analyses

Secondary Endpoint Analyses

Event counts over 60 days will be analyzed by Poisson regression as described above in 8.4. Time

to events will be analyzed by Cox regression. Differences between belnacasan and placebo with

respect to change in continuous endpoints will be assessed by mixed effects models for continuous

repeated measures data and mixed effects logistic models for repeated categorical variables.

Endpoint proportions of belnacasan and placebo groups will be assessed by contingency table

analysis (chi-square).

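### The Cox analyses of time to recovery name no covariates for days since symptom onset or baseline symptom burden; prespecifying both would be a cheap gain if they are prognostic

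*Combined protocol and SAP*

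**What the plan says.** Section 8.2 assigns "Cox proportional hazards regression for time-to-event data", and Section 8.5 repeats that time "to events will be analyzed by Cox regression". Neither names a covariate or stratum. Section 8.3 uses baseline disease characteristics for description only. The illustrative table in 12.3 is a single sequential A/B list, and no stratification is stated elsewhere.

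Endpoint 1c (Section 3.4) compares the "number of days from randomization to the first day of achieving each item in 1a and 1b above". Endpoint 4c counts days from enrollment to a sustained one-point improvement on the ordinal scale.

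Section 5.3 admits a subject with "Subject has evidence of either mild or moderate COVID-19 illness of less than 7 days from first onset, with minimal baseline symptom severity". One entry route needs at least two listed symptoms, up to and including "shortness of breath with exertion (without supplemental oxygen requirement) with a score of 2 or higher", with a lower threshold for smell or taste. The other needs one symptom plus clinical evidence of moderate disease. Table 1 schedules "Symptoms assessment" at the screening/enrollment visit. Under Section 5.1, PCR confirmation may put completion of enrollment 1 to 3 days later.

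Section 8.7 says the trial will likely lack power for clinically meaningful differences and is meant to supply an effect size for a larger trial.

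**The concern.** Section 1.3 puts an uncomplicated illness at up to 12 to 15 days. An entry spread of 0 to 6 days is 6/15 = 40% to 6/12 = 50% of that course. A subject randomized late in a self-limiting illness can be expected to reach recovery sooner after randomization than one randomized at onset, whatever the drug does. Symptom burden at entry may act similarly.

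Two things are at stake. If these factors are prognostic, leaving them out of a Cox model pulls the treatment hazard ratio toward 1 and costs power. With 20 per arm, chance differences in disease stage can also move the single estimate that the next trial will be planned on. Because the plan is silent, the choice of model would remain open after the data are seen, and an adjustment made then would look data-driven.

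**Working it through.** **1. The plan's own figure.** Section 8.7 says differences in rate ratios must exceed 60% for 80% power at alpha 5% with 20 per arm. No event count or sidedness is given; I assume two-sided 5% and nearly all 40 subjects having an event.

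- Schoenfeld: HR = exp(−(1.960 + 0.842)/√(d/4)). With d = 40, exp(−2.802/3.162) = 0.412, a 58.8% reduction. With d = 36, 0.393, or 60.7%.
- Freedman, d = 40: c = √40/2.802 = 2.257; HR = (c − 1)/(c + 1) = 0.386, or 61.4%.

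The figure is therefore reproduced as an unadjusted comparison. A 60% reduction is HR 0.40; inverted to a recovery benefit it is 1/0.40 = 2.5, the effect assumed below.

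**2. Chance imbalance with 20 per arm.**

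- If days since onset were uniform on the integers 0 to 6 (assumption), the variance is (7² − 1)/12 = 4 and the SD is 2 days. The between-arm difference in means has SD 2 × √(2/20) = 0.63 day, and is at least 1 day in about 12% of trials.
- For any covariate in SD units, the difference has SD √(2/20) = 0.316. P(|difference| > 0.3 SD) = 34%; for at least one of two independent covariates, 1 − 0.657² = 57%. Above 0.5 SD the figures are 11% and 21%.

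**3. Power, by simulation.** Assumptions: 20 per arm, true HR 2.5, exponential recovery times with placebo median 14 days, censoring at day 60, two independent standard-normal covariates of equal strength, 3,000 trials per row, about 36 to 39 events.

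| HR per SD of each covariate | Power unadjusted | Power adjusted | Median HR unadjusted | Median HR adjusted |
|---|---|---|---|---|
| 1.00 (none) | 76% | 75% | 2.50 | 2.59 |
| 1.22 | 72% | 75% | 2.42 | 2.65 |
| 1.42 | 65% | 76% | 2.24 | 2.66 |
| 1.65 | 55% | 75% | 2.03 | 2.61 |
| 2.01 | 45% | 73% | 1.88 | 2.61 |

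The losses are about 3, 11 and 20 points for weak, moderate and strong prognosis; the last row, a very strong assumption, gives 28.

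A second design (Weibull shape 1.5, scale 10 days, censored at day 28) gives a similar picture. Prognosis is the log hazard per SD of score / per day since onset, and ranges are across repeated runs:

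- None: 77–78% unadjusted, 76–77% adjusted.
- 0.2/0.05: 75% to 76%.
- 0.3/0.1: 68–70% to 74–77%.
- 0.5/0.1: 60–66% to 74–76%.
- 0.7/0.15: 52–56% to 74–76%.

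**4. What adjustment does to the estimate.** In the first design at HR 2.5, the SD of the log HR rises from about 0.38 to 0.41. The power gain therefore comes from removing attenuation, not from precision. In the second design the mean adjusted log HR is 0.98 to 1.01 against ln 2.5 = 0.92, a small upward bias; the mean unadjusted value is 0.87, 0.81 and 0.72 in the last three scenarios.

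**5. Type I error.** First design: 4.8–5.6% unadjusted, 5.6–6.3% adjusted. In the second, prognostic scenarios gave about 5–7% adjusted; one 1,500-trial run with unrelated covariates gave 8.0% against 6.7% unadjusted.

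**6. Imbalance and the single estimate.** With no drug effect, in the 10% of second-design trials whose imbalance most favors belnacasan, the median unadjusted HR is 1.23 to 1.34; adjusted, it is 0.95 to 0.98.

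**The case against.** The best case for leaving the plan alone is that these are secondary endpoints in a trial that openly disclaims power. Randomization already protects the unadjusted test, and the baseline tables would reveal an imbalance. Adjustment brings a slightly inflated, more variable estimate to a trial whose purpose is estimation. The unadjusted hazard ratio is a legitimate marginal quantity rather than a wrong one. If prognosis is weak the gain disappears, and at a true HR of 1.5 power is only about 18–22% unadjusted and 24–25% adjusted. All of this stands; it limits the size of the point without removing it.

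Some stronger readings are tempting but unsupported:

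- A reader might infer that 8.5 prescribes a treatment-only model. It does not; it is silent on covariates.
- A reader might infer that the unadjusted test is biased or inflates false positives. Type I error stays near 5%; imbalance affects how one estimate is read, not the error rate on average.
- A reader might infer that adjustment removes noise. In the Cox model the SD of the log HR rises.
- A reader might infer that both covariates are already collected in usable form. Eligibility needs only a judgement that onset was under 7 days ago, and no onset date is listed as a data item. No total symptom score is defined, and the diary excerpts in 12.2 mix severity grades, frequency counts and a three-level smell/taste item.
- A reader might extend the remedy to every Cox endpoint. The 2b time endpoints are limited to subjects with early fever or with SpO2 above 93% and below 96% at entry. With an assumed 6 per arm, adjusting raises the SD of the log HR from 0.76 to 1.07 and null rejection from 5.5% to 8.3%, and the mean estimate is about 3.3 for a true 2.5.

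For 4c, the starting ordinal level also bounds the possible improvement, which neither covariate fully captures.

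**Conclusion.** The concern holds as a modest, inexpensive improvement. Neither the Cox specification nor the illustrative randomization scheme accounts for disease stage or symptom burden at entry. At an assumed HR of 2.5 with most of the 40 subjects recovering, an unadjusted model loses about 1 to 20 points of power from weak to strong prognosis, and more only under a very strong assumption. If the factors are not prognostic, adjusting costs about 1 point. Prognostic strength, HR 2.5 and the recovery-time distributions are assumptions; the documents supply none of them.

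The effect estimate is the more lasting reason to act. Section 8.7 intends it for planning a larger trial, and with 20 per arm a difference above 0.3 SD on a given covariate arises by chance in about one trial in three. The primary safety analysis is untouched.

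**What to change.** In Section 8.5, prespecify that the Cox models for 1c, and for 4c if most subjects have events, include two continuous covariates: days from symptom onset to randomization, and a baseline symptom score. Report the unadjusted hazard ratio alongside.

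Two definitions are needed. Record the onset date at screening and measure the interval to randomization, since PCR confirmation can delay enrollment. Define the score from the enrollment symptom items, stating how the different response scales are combined.

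Leave the 2b fever and SpO2 subset endpoints and 3b time to hospitalization unadjusted, because subjects or events may be few.

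The cost is SAP wording, one date field and a scoring rule. The statistical price is a hazard ratio conditional on the covariates, a slightly larger SD of its log (about 0.41 against 0.38), a small upward small-sample bias, and null rejection of about 6%.

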1.3 Dosing rationale

Belnacasan (VX-765/RVT-201/MSR-001) has previously been studied in rodents and large animals including dogs and monkeys to doses of up to 2000mg/kg/day for toxicity studies in dogs. Dosing at these levels and in multi-dosing schedules have not shown any severe and particularly life-threatening side effects. In human trials, including for conditions such as seizure disorders, the drug has been trialed in increments of 300mg/dose on a TID or QID regimen up to 900mg QID for 13 weeks, in nearly 100 patients.

Detailed pharmacokinetic studies from Vertex / Roivant are available for review. In brief, ex-*vivo* studies have demonstrated that Lipopolysaccharide stimulated IL-1β production is 50% suppressed by the active metabolite of belnacasan at a concentration of 0.8mcg/ml. This translated in to 50% suppression of IL-1β by single oral dose of 400mg while 80% suppression was achieved with doses of 800 and 1600mg. There was gradual but marked inhibition of IL-18 over 14 days in healthy controls as compared to placebo and 60% inhibition with 900mg TID as well as 1200mg TID and 1800mg TID during the duration of the study. For this study we have therefore chosen our primary dose as 900mg TID in the absence of data on acute viral infection / COVID-19.

The drug has previously been manufactured with appropriate due diligence in tablet form at 300mg/tablet (Data available from Roivant Sciences) and will be manufactured by the same compounding pharmacy (Metrics), in the original format for immediate use in this trial.

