Heart: troponin; Kidney: creatinine, blood urea nitrogen (BUN), electrolytes (calcium, carbon dioxide, chloride, potassium, sodium, magnesium); Pancreas: glucose, HbA1c, lipase; Liver: ALT, AST, ALP, total bilirubin; Muscle weakness: creatinine kinase; Hematology: red blood cell count, hemoglobin, platelet count, prothrombin time (PT), partial thromboplastin time (PTT), ddimer; Immunology: white blood cell count, neutrophils, lymphocytes, monocytes, eosinophils, T cells, SARS-CoV-2 viral load in nasopharyngeal sample, SARS-CoV-2 serology in blood; Inflammation: CRP, ferritin, LDH, caspase-1, IL-18, IL-1β, IL-1 receptor antagonist, gasdermin D, IL-6, TNF-α, G-CSF

- *5a) Analysis and comparison of* surrogate markers of COVID-19 related inflammation and organ involvement as determined by biochemistry, hematology, and immunology labs and studies, in treatment group versus placebo group, respectively, for
 - o values on days 1 (enrollment), 7, 14, 21, 28 post randomization
 - o changes from enrollment to days 7, 14, 21, or 28 post randomization
 - o changes between days 7, 14, 21, 28 post randomization
- *5b) Reference range rates:* proportion of treatment group versus placebo group, respectively, who experience normal / in-range values for a given marker at days 7, 14, 21, 28 post randomization

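### Section 8.5 fixes no analysis scale or baseline covariate for the endpoint 5 concentration markers, so by default a proportional drug effect is tested as unadjusted raw change, at a cost in power that depends on a skewness the documents do not give

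*Combined protocol and SAP*

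**What the plan says.** Section 8.5 is the only inferential rule for continuous secondary endpoints. Differences between arms with "respect to change in continuous endpoints will be assessed by mixed effects models for continuous" repeated-measures data. No scale, transformation or baseline covariate is named, either there or in the general methods of section 8.2.

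Section 8.2 summarizes continuous variables by arithmetic mean, SD, median and range. Where applicable it adds the "number of observations above the limit of quantification". It has no geometric mean. Neither 8.5 nor the missing-data section 8.6 says how a value below that limit would enter a model.

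Section 3.4, area 5, lists the markers. They include "CRP, ferritin, LDH, caspase-1, IL-18", further cytokines, D-dimer and "SARS-CoV-2 viral load in nasopharyngeal sample". Endpoint 5a compares values at each visit, "changes from enrollment to days 7, 14, 21, or 28 post randomization", and changes between visits. Endpoint 5b compares the proportion of subjects "who experience normal / in-range values for a given marker at days 7, 14, 21, 28 post randomization".

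Section 1.3 states the pharmacodynamic effect in proportions: 50% and 80% suppression of IL-1β, and for IL-18 "60% inhibition with 900mg TID as well as 1200mg TID and 1800mg TID". The IL-18 data are from healthy controls. The 900 mg TID dose is then chosen on these data together.

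**The concern.** A drug that suppresses a marker by a fixed percentage has a constant ratio effect. It lowers a high value by much and a low value by little in absolute terms. On the log scale this is one common shift. On the raw scale it is a difference that varies with the subject's level. If the marker is also right-skewed, a few high values drive both the mean change and its variance, and with 20 per arm they can hide a real proportional effect.

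The second issue is the change score. Subtracting baseline without also adjusting for it carries all the baseline noise into the outcome.

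What is at stake is the estimate. The secondary objective (3.3) is effect size, and section 8.7 says the trial is to inform a larger one. A raw mean difference in a skewed marker depends on how high the sampled baselines were, so it carries over poorly to another population. A scale that is not fixed in advance can also be chosen after the data are seen.

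**Working it through.** **The plan's own figure.** Section 8.7 gives a difference of over 60% in endpoint rate ratios for 80% power. It concerns rates, and it cannot be rebuilt from the documents alone because no event rate or sidedness is given. It is plausible under some inputs: with a two-sided 5% test, the Schoenfeld formula gives a hazard ratio of 0.412 if all 40 subjects have an event. It does not bear on biomarkers, and no biomarker power is stated, so there is nothing further to reproduce.

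**Inputs from the documents.** 20 per arm and alpha 5% (8.7); 60% inhibition, that is ratio 0.40 and log difference ln 0.4 = −0.916 (1.3); post-baseline visits on days 7, 14, 21 and 28 (3.4).

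**Assumptions.** Lognormal values, log-SD s from 0.5 to 1.5, correlation ρ = 0.6 between visits (range 0.4 to 0.8), placebo flat over time, two-sided test, no dropout.

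**Step 1: log change, one visit.** The SD of log change is s√(2(1−ρ)) = 0.894s, and the standard error of the arm difference is 0.894s√(2/20).
- s = 0.5: 0.916/(0.447 × 0.316) = 6.48, power about 100%.
- s = 1.0: 0.916/(0.894 × 0.316) = 3.24, power about 88%.

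**Step 2: raw change, one visit, median baseline set to 1.** The mean difference is 0.6·exp(s²/2). The variance of change is 2e^(s²)(e^(s²) − e^(ρs²)) on placebo and e^(s²)[1.16(e^(s²) − 1) − 0.8(e^(ρs²) − 1)] on drug.
- s = 0.5: difference 0.680; variances 0.314 and 0.257; standard error √(0.571/20) = 0.169; ratio 4.03.
- s = 1.0: difference 0.989; variances 4.87 and 3.63; standard error √(8.50/20) = 0.652; ratio 1.52.

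At s = 1.0 the signal relative to its standard error is therefore 1.52 on the raw scale and 3.24 on the log scale. Raw change is not normal, so its power was simulated.

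**Step 3: simulated power, one visit.**

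| log-SD | raw change | log change |
|---|---|---|
| 0.5 | 98% | 100% |
| 0.8 | 65% | 97% |
| 1.0 | 43% | 89% |
| 1.2 | 26% | 74% |
| 1.5 | 14% | 55% |

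Repeat runs differ by about two points or less. Over correlations of 0.4 to 0.8, raw power as a fraction of log power is 0.93 to 1.00 at log-SD 0.5, 0.45 to 0.63 at 1.0 and 0.26 to 0.28 at 1.5. With ratio 0.5 and log-SD 1.0, power is 31% versus 66%.

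**Step 4: closer to the planned model.** With complete data and equal correlations, the treatment main effect of a mixed model is the comparison of post-baseline means. At log-SD 1.0 and correlation 0.6:

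| analysis | raw | log |
|---|---|---|
| one visit, change | 43% | 89% |
| one visit, baseline as covariate | 73% | 93% |
| mean of four visits, change | 58% | 98% |
| mean of four visits, baseline as covariate | 95% | 100% |

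**Step 5: placebo not flat.** If placebo values halve as subjects recover, the raw difference halves too, while the log difference stays at −0.916. Raw change then keeps 0.49 to 0.64 of the log power at log-SD 0.5, and 0.18 to 0.20 at 1.0.

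**Step 6: no drug effect.** Raw change rejects in about 3% to 5% of trials, log change in about 5%.

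**The case against.** The strongest reply is that the text is silent, not wrong. Section 8.5 names a class of model and neither requires nor rules out a log transform. A reader might infer that the plan prescribes the raw scale. It does not: raw change is only the default reading, and the point is worded that way.

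A reader might also infer that the trial will lose about half its power to detect the IL-18 effect. The documents do not support that. They give no SD, skewness or correlation for any marker. A halving needs a log-SD near 1.0 with flat placebo, or near 0.5 if placebo values halve. At log-SD 0.5 with flat placebo the loss is negligible. The one-visit change score is also harsher than the planned repeated-measures model: with four visits and a baseline covariate, raw power at log-SD 1.0 is already 95%. This stands as a limit on the size of the claim. It does not remove the gap, because 8.5 names no baseline covariate.

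Other parts of the reply also stand:
- The 60% comes from healthy controls, and IL-1β supported the dose as well.
- Area 5 is one of five secondary areas in a hypothesis-generating trial whose low power section 8.7 admits.
- Visit values (5a) and in-range proportions (5b) are read out too, and 5b does not depend on scale.
- Section 8.2 includes median and range, and its limit-of-quantification count applies only where relevant.

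The admitted low power is a weaker defence. It concerns the number of subjects, whereas this loss can be avoided with the same subjects. Endpoint 5b does not estimate a proportional effect.

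**Conclusion.** The point holds as a gap with a near-free remedy. As written, 8.5 leads by default to unadjusted raw change for markers whose expected drug effect section 1.3 states as a ratio. Under the stated assumptions the one-visit cost runs from nothing material at log-SD 0.5 (98% versus 100%) to 43% versus 89% at 1.0 and 26% versus 74% at 1.2. With four visits at log-SD 1.0 it is 58% versus 98%. Scale and missing baseline adjustment share the blame: with baseline as covariate the four-visit gap at log-SD 1.0 shrinks to 95% versus 100%.

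These figures rest on lognormality, the assumed SDs and correlation, complete data, and a healthy-control effect carried over to COVID-19 patients. A reader might fear false positives. There is no sign of that, since raw-scale type I error stays at or below about 5%. The harm is lost power and an estimate that is hard to carry into a larger trial. The plan should be changed, but the primary safety objective is not affected.

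**What to change.** In section 8.5:
- For cytokine and inflammasome markers and other positive, right-skewed concentrations (such as CRP, ferritin and D-dimer, and viral load if reported as copies), model log-transformed post-baseline values in the planned mixed model, with log baseline as covariate. The condition on viral load is needed because Table 1, footnote 3, accepts any approved or commercial RT-PCR method and so does not fix the unit.
- Report ratios of geometric means with 95% confidence intervals, and add geometric means to the summaries in 8.2.
- Treat any value below the limit of quantification as left-censored, or as half the limit with a censored-likelihood check.
- Keep the raw scale, with baseline as covariate, for roughly symmetric markers.
- List the markers in each group before unblinding, since the documents do not describe their distributions.

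The cost is SAP wording and programming, with no added subjects, visits or samples. The small downside is that effects are reported as ratios and not as absolute differences.
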